6.1.7.2. Subjective Units of Distress Scale (SUDS)

The SUDS, used at Visit 2 (Baseline) and Visit 3 (Treatment) as part of each public speaking challenge, is scored 0 to 100. It is a standard instrument for rating social and performance anxiety in patients with SAD during role-playing situations. Scores are operationalized for subjects in this study as 0=totally relaxed or no anxiety100=most distress or anxiety imaginable.

- Average SUDS Score = Sum of SUDS scores recorded at divided by the number of SUDS scores recorded during the speech performance. For complete data, there should be SUDS scores collected.
- Proportion SUDS Responders = Proportion of subjects with an improvement of 20 or more points in average SUDS scores from Visit 2 (Baseline) to Visit 3 (Treatment).
- Fraction of Missing Change from Baseline in Average SUDS Scores = Number of
 missing values of change from baseline to Visit 3 (Treatment) average SUDS scores
 across all subjects in the ITT Population divided by the total number of expected change
 scores (1 per subject). The fraction of missing change from baseline in average SUDS
 scores is used to compute the threshold for determining whether to implement the
 multiple imputation procedure.

6.1.7.3. Clinical Global Impression Scale of Improvement (CGI-I)

[figure not shown]
The CGI-I is a clinician-rated instrument that measures the clinician's evaluation of change in subjects' overall improvement with treatment. Clinicians will respond to the following question:

"Please choose the response that best describes how anxious you felt the subject was during the second speech compared to how anxious they appeared in the first speech a week ago.

AD-ST-33.06 Effective date: 12-Nov-2020

Version Final 1.0 | Date 28-Jun-2022 | AD-ST-33.06 Effective date: 12-Nov-2020 | Page 24 of 140

[figure not shown]

• **Proportion of CGI-I Responders** = Proportion of subjects with a score of 1 (Very much less anxious) or 2 (Much less anxious) on the CGI-I at Visit 3 (Treatment).

6.1.7.4. Patient Global Impression of Change (PGI-C)

The PGI-C is a self-administered instrument that measures change in subjects' overall improvement with treatment. Subjects will respond to the following question:

"Please choose the response that best describes how anxious you felt giving the second speech compared to how anxious you felt giving the first speech a week ago.

The derived variable from this assessment will be the following:

• **Proportion PGI-C Responders** = Proportion of subjects with a score of 1 or 2 on the PGI-C at Visit 3 (Treatment).

6.1.7.5. Liebowitz Social Anxiety Scale (LSAS)

The LSAS is a clinician-rated scale that has been shown to be sensitive to treatment-related change in social anxiety symptoms. The time frame for rating symptomatology is the past week. The scale consists of 24 items. Each item is given 2 ratings: fear or anxiety on scale of 0 to 3 and avoidance on a scale of 0 to 3, with a total maximum overall score of 144. The "Total Performance (P) Subscore – Fear or Anxiety" and the "Total Performance Subscore (P) – Avoidance" are the sums of the fear or anxiety or avoidance scores, respectively, on items 1-4, 6, 8, 9, 13, 14, 16, 17, 20, and 21. The "Total Social (S) Subscore – Fear or Anxiety" and "Total Social (S) Subscore – Avoidance" are the sums of the fear or anxiety or avoidance scores, respectively, on items 5, 7, 10-12, 15, 18, 19, and 22-24. The "Total Anxiety Subscore" and the "Total Avoidance Subscore" are the sums of performance and social subscores for fear or anxiety and avoidance scales, respectively. The LSAS total score for each subject is the sum of all ratings across both scales.

The derived variables for this assessment are the following:

6.1.7.7. Hamilton Depression Scale (HAM-D)

At Visit 1 (Screening) and Visit 4 (Follow-Up), subjects will be asked to complete the clinicianrated HAM-D questionnaire to assess depression. The HAM-D questionnaire consists of 17 items, each scored on either a 3- or 5-point scale.

The Hamilton Depression Scale (HAM-D) total score is calculated as the sum of the 17 individual item scores and ranges from 0 to 52.

6.1.7.8. Columbia-Suicide Severity Rating Scale (C-SSRS)

The C-SSRS is a semi-structured interview that captures the occurrence, severity, and frequency of suicide-related thoughts and behaviors during the assessment period. The interview includes definitions and suggested questions to solicit the type of information needed to determine if a suicide-related thought or behavior has occurred. The C-SSRS has a "baseline" version, which will be completed at Visit 1 (Screening), and a "since last visit" version that will be completed at all subsequent visits.

There are a maximum of 19 items to be completed: 7 that are required, 10 potential additional items if there is a positive response to a required item, and 2 items for suicide/suicide behavior present during the interview. The C-SSRS uses dichotomous scales (i.e., yes or no), Likert scales, and text or narrative are used to further describe the thoughts or behaviors.

Subjects are considered to have had suicidal ideation during a time period (lifetime, last 6 months, since last visit) if they respond "Yes" to any of the 5 suicidal ideation questions listed below for that time period:

- Wish to be dead (Category 1)
- Non-specific active suicidal thoughts (Category 2)
- Active suicidal ideation with any methods (Category 3)
- Active suicidal ideation with some intent to act, without specific plan (Category 4)
 Active suicidal ideation with specific plan and intent (Category 5)

Subjects are considered to have had suicidal behavior during a time period if they respond "Yes" to any of the 5 suicidal behavior questions listed below for that time period:

- Completed suicide
- Actual attempt
- Interrupted attempt
- Aborted attempt
- Preparatory acts or behavior

Subjects are considered to have suicidal ideation or behavior during a time period if they responded "Yes" to any of the suicidal ideation or behavior questions for that time period.

A subject's maximum suicidal ideation score is the maximum suicidal ideation category to which they responded "Yes".

6.1.8. Data Adjustments/Handling/Conventions

All collected data will be presented in listings. Data not subject to analysis according to this plan will not appear in any tables or graphs but will be included only in the data listings.

[figure not shown]
All P values will be displayed in 4 decimals and rounded using standard scientific notation (e.g., 0.XXXX). If a P value less than 0.0001 occurs it will be shown in tables as < 0.0001; similarly, if a P value greater than 0.9999 occurs, it will be shown in tables as > 0.9999.

Medical history and AEs (all types) will be coded using the most recent version of the Medical Dictionary for Regulatory Activities (MedDRA), version 24.1. Prior and concomitant medications will be coded using the World Health Organization Drug Dictionary (WHO-DD) Enhanced Anatomical Therapeutic Chemical (ATC) classes and preferred terms, version WHODrug B3 Global Sep 2021.

For quantitative laboratory values reported as '<X' or ' \le X', 1/2 times the lower limit of quantitation will be used for analysis. For quantitative laboratory values reported as '>X' or $\geq X'$, 3/2 times the upper limit of quantitation will be used for analysis.

If partial dates occur for treatment emergent AEs, prior medications, or concomitant medications, the convention for replacing missing information for the purpose of statistical analysis is as follows.

Adverse Events

- If the event start date is missing day and month, the treatment start date is not missing, and event start year is the same as the treatment start year, set the event start date to the treatment start date.
- If the event start date is missing day and month and the treatment start date is missing, the event start year is not the same as the treatment start year, or if there is information indicating that the event ended before the treatment start date (e.g., the event end date is before the treatment start date), then set the event start month and day to January 1st.
- If only the event start day is missing, the treatment start date is not missing, and the event start month and year are the same as the treatment start month and year, set the event start day to the treatment start day.
- If only the event start day is missing and the treatment start date is missing, or the event start month and year is not the same as the treatment start month and year, or if there is information to indicate that the event ended before the treatment start date, then set the event start day to the first day of the start month.
- End dates will not be imputed.

Prior and Concomitant Medications

Medication start and stop dates will not be imputed. Instead, available information will be used to assign the following categories to each medication: 1) prior versus concomitant versus both, 2) occurring before versus after Visit 3 (Treatment). If a missing date part leads to uncertainty in how to assign categories, the medication will be considered concomitant and to have been taken after Visit 3 (Treatment) dosing.

For example, if the medication start year or end year is after the start of treatment, the medication will be considered concomitant even if the start month and/or day are missing. Likewise, if the medication start year occurs in the same year as the treatment start year, and the medication start month or end month is after the treatment start month, then the medication will be considered concomitant even if the medication start or end day is missing.

7. Study Subjects and Demographics

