6.1.1. Baseline

Baseline for each study assessment is defined in Table 2.

Table 2: Baseline Definitions

Parameter	Baseline
Safety Variables (clinical laboratory assessments, vital signs, ECGs, physical examinations)	The last non-missing assessment before the first dose of study drug given at Visit 2 (Baseline).
C-SSRS Scores	Scores on the Baseline version of the C-SSRS given at Visit 1 (Screening).

divided by the number of SUDS scores recorded during the speech performance.

Average Anticipatory SUDS Score

Sum of Visit 2 (Baseline) SUDS scores

divided by the number of recorded SUDS scores.

LSAS total score, HAM-D total score.

Total score at Visit 1 (Screening).

Abbreviations: CGI-I = Clinical Global Impression of Improvement; ECG = electrocardiogram; C-SSRS = Columbia-Suicide Severity Rating Scale; Scale; LSAS = Liebowitz Social Anxiety Scale; PGI-C= Patient Global Impression of Change; SUDS = Subjective Units of Distress Scale

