9.1. Adverse Events

Treatment emergent AEs (TEAEs) are defined as:

- AEs with onset at the time of or following the start of treatment with IP through Visit 4 (Follow-Up) or
- AEs starting prior to the start of treatment with IP but increasing in severity or relationship at the time of, or following, the start of treatment with IP through Visit 4 (Follow-Up).

Any medical condition that is present at the time that the subject is screened will be considered as baseline and not reported as an AE. However, if the study subject's condition deteriorates at any time during the study, it will be recorded as an AE.

The Investigator will record all reportable events with start dates occurring any time after informed consent is obtained until 7 days after the last day of study participation. Events will be followed for outcome information until resolution or stabilization. Missing and partially missing start dates will be imputed for the purpose of analysis as described in Section 6.1.8.

All AEs, TEAEs, and serious AEs (SAEs) will be coded using the MedDRA dictionary, as discussed in Section 6.1.8.

All AE data will be summarized for 2 periods: before Visit 3 (Treatment) dosing and during or after Visit 3 (Treatment) dosing. The reporting is done in this manner due to the difference in study drug exposure during these 2 periods. All subjects will receive placebo at Visit 2 (Baseline), and all subjects will receive their randomized treatment at Visit 3 (Treatment). Thus, between Visit 2 (Baseline) up to dosing at Visit 3 (Treatment), subjects will have only been exposed to placebo. From Visit 3 (Treatment) dosing and onward, subjects will have been exposed to either active drug (PH94B) or placebo.

All AE data will be categorized as Severe > Moderate > Mild. Relationship of all AEs to IP will be categorized as related or not related. In the summaries showing severity and relationship to study drug, the event with the maximum severity or strongest relationship to study drug will be reported. For the purposes of analysis, if a particular event is missing the severity, it will be categorized as severe, and it if it missing the relationship, it will be categorized as related.

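### Partial adverse-event start dates are imputed without reference to the Visit 3 dose, so post-Visit 3 events with incomplete dates are mostly tabulated as pre-Visit 3, in both arms

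*SAP*

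**What the plan says.** SAP 6.1.8 gives four rules for a partial AE start date:

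- Day and month missing, year equal to the treatment start year: "set the event start date to the treatment start date".
- Day and month missing, year different: "then set the event start month and day to January 1st".
- Only the day missing, month and year equal to those of treatment start: "set the event start day to the treatment start day".
- Only the day missing, month or year different: "then set the event start day to the first day of the start month".

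The calendar defaults in the second and fourth rules also apply when treatment start is missing or the event is known to have ended before it. None of the four rules refers to Visit 3.

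SAP 9.1 states that partial start dates are imputed for analysis under 6.1.8, and then: "All AE data will be summarized for 2 periods: before Visit 3 (Treatment) dosing and during or after Visit 3 (Treatment) dosing". Its reason is that exposure before Visit 3 dosing is to placebo only.

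For a medication whose incomplete date leaves its category in doubt, SAP 6.1.8 says that "the medication will be considered concomitant and to have been taken after Visit 3 (Treatment) dosing". SAP 9.1 counts an AE with missing severity as severe and one with missing relationship as related.

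**The concern.** The AE tables are cut at Visit 3 dosing, but the date rule is anchored elsewhere. An event with an incomplete date that began after the randomised dose can be given a start date a week earlier, on the day when every subject took placebo. It is then reported in the wrong period. The SAP's other conventions for missing safety information resolve doubt towards the randomised dose or towards the worse category; this one does the opposite. At stake are the AE rates after the randomised dose, which are the part of the safety summary that describes exposure to PH94B.

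**Working it through.** The documents give no figure for this point, so there is none to reproduce.

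**Step 1: what treatment start means.** SAP 6.1.8 does not define it. The evidence for Visit 2 is:

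- SAP Table 2 places the first dose of study drug at Visit 2, and SAP 7.4 says that all Visit 2 vials are placebo.
- SAP 9.6 counts medications as concomitant from Visit 2.
- The protocol synopsis describes an eight-day treatment period with dosing at Baseline.
- SAP 9.1.1 and 9.1.2 tabulate treatment-emergent events before Visit 3 dosing. If treatment began at Visit 3, that period could hold only earlier events that later worsened.

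**Step 2: share misplaced.** Inputs are Visit 3 at Visit 2 + 7 days and Visit 4 at Visit 3 + 7 days (protocol 10.2.2 and 10.2.3). Assumptions are a Visit 2 date uniform over 365 days and a true onset either on the Visit 3 day or uniform over the 8 days from Visit 3 to Visit 4.

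The imputed date is correct only if a first of the month (or, with the month also missing, a January 1st) falls between Visit 3 and onset inclusive. For onset i days after Visit 3 that covers i + 1 calendar days. For i = 0 to 7 the mean is 4.5.

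| Missing part | Onset | Correctly placed | Misplaced |
|---|---|---|---|
| Day | Visit 3 day | 12 × 1/365 = 3.3% | 96.7% |
| Day | Uniform | 12 × 4.5/365 = 14.8% | 85.2% |
| Day and month | Visit 3 day | 1/365 = 0.3% | 99.7% |
| Day and month | Uniform | 4.5/365 = 1.2% | 98.8% |

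By branch, for day missing and uniform onset:

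- Onset in the Visit 2 month (65.5% of cases) is always misplaced.
- Onset in a later month (34.5%) goes to the first of the month and is misplaced in 57.1%.
- Together: 0.655 × 1 + 0.345 × 0.571 = 0.852.

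Enumerating all visit intervals of 5 to 9 days gives the same shares. The reverse error, a true pre-Visit 3 event dated on or after Visit 3, is 0%. If treatment start meant Visit 3, misplacement would also be 0%.

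**Step 3: effect on rates.** Observed rate = p × (1 − f × m). Here p is the true post-Visit 3 rate, f the share of subjects with a post-Visit 3 event whose only such event has a partial date, and m the misplaced share. The documents give neither p nor f, so both are assumed. With p = 20% (20.8 of 104 per arm):

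| f | m = 0.852 | m = 1 (upper bound) | Subjects lost at m = 1 |
|---|---|---|---|
| 1% | 19.8% | 19.8% | 0.2 |
| 5% | 19.1% | 19.0% | 1.0 |
| 10% | 18.3% | 18.0% | 2.1 |

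**Step 4: between arms.** Take true rates of 20% and 10%, with f = 5% and m = 1 in both arms. The observed rates are 19.0% and 9.5%. The difference falls from 10 to 9.5 points and the ratio stays at 2.0.

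**The case against.** Four arguments on the other side carry weight.

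- **The anchor is inferred.** SAP 6.1.8 does not define treatment start, SAP 6.1.7.1 uses a different phrase (the first dose of study drug) for study day, and Visit 3 is labelled Treatment throughout. This stands as a qualification. The indications in Step 1 nonetheless leave Visit 2 as the only workable reading.
- **Partial dates should be rare.** Protocol 11.2.3 asks for start date and time, protocol 11.2 asks about events at each visit, visits are about a week apart, and sites must resolve queries. This stands. The 85% and 99% are conditional on a date being partial. One event moves an arm's rate by 1/104, about 1 percentage point, only if it is that subject's sole relevant event.
- **The rule acts on both arms.** This stands. A reader might infer that PH94B events are transferred to the placebo arm, or that the comparison is tilted only in the drug's favour. The documents do not support either. SAP 9.1.1 and 9.1.2 tabulate by period and treatment group, so the event stays in its own column under the earlier period, and SAP 9.1 keeps it in the listings. The placebo arm's post-Visit 3 rate shrinks too.
- **A bare default to Visit 3 would err the other way.** Of day-missing events with true onset between Visits 2 and 3, the known month alone rules out a post-Visit 3 onset in only 12 × 4/365 = 13%. The other 87% would move to the later period in both arms, which adds background events and pulls the risk ratio towards 1. This stands, and it governs the form of the fix.

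**Conclusion.** The rule is wrong as written. It misplaces most partial-date events that truly began after Visit 3 dosing, it never errs in the other direction, and it conflicts with the SAP's own medication rule and its worst-case rules for severity and relationship. The shares (about 85% with the day missing, about 99% with day and month missing, 57% in the first-of-month branch) rest on treatment start meaning Visit 2 and on onset uniform between Visits 3 and 4. For onset on the Visit 3 day itself they are higher.

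The consequence is understated post-Visit 3 rates in both arms. If partial dates are equally frequent in each, the risk difference is attenuated and the risk ratio is unchanged. The expected size is small: at most 0.2 to 2.1 subjects per arm over the assumed range. Safety is summarised descriptively, so no formal test is affected. It is worth correcting because the error runs one way and the correction is inexpensive.

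**What to change.** In SAP 6.1.8, before unblinding:

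1. Define the treatment start date.
2. Assign the AE period first from the visit and time point at which the event was recorded, the known date parts and the stop date. Protocol 10.2.3 has AEs reviewed at Visit 3 both before randomisation and after the speaking challenge, so the time point can separate the two periods. Confirm that the AE form captures it; the documents do not say.
3. Only if doubt remains, set the start to the Visit 3 dose date and place the event in the period during or after Visit 3 dosing. This matches the medication rule.
4. Add a sensitivity table with the unresolved events allocated to the earlier period.

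The cost is a few lines of SAP text and programming, plus one table. The SAP was written to protocol Version 3.0 and states that no interim analysis is planned, while the current protocol adds one, so a revision is due in any case. The downside is that some truly pre-Visit 3 events that the recording visit does not resolve will move to the later period, in both arms alike. The sensitivity table shows how much that matters.

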7.1. Disposition of Subjects and Withdrawals

The numbers of subjects randomized, completing, withdrawing (including reasons), and assigned to each analysis population will be tabulated by treatment group and overall for the All Subjects population.

7.2. Protocol Violations and Deviations

Protocol deviations will be tracked, recorded, and reviewed prior to database lock, following the Protocol Deviation Guidance Plan for this study. The deviation list will be stored in the Remarque system and transferred to the biostatistics team for analysis.

Protocol deviations will be classified as "Important" or "Non-Important". An important deviation poses a possible safety issue to the participant, or it has a potential impact on the statistical analysis of the clinical data. A non-important deviation is identified as any protocol deviation that does not meet the criteria for an important deviation.

Important deviations include but are not limited to:

- Violation of inclusion/exclusion criteria
- Randomization or dosing error
- Use of prohibited medications
- Assessment conducted by unqualified personnel
- Missing baseline efficacy or safety assessments

Non-important deviations include but are not limited to:

- Lack of data collection due to subject non-compliance
- Subjects who fail to make scheduled visits
- Extension of screening period to clarify diagnoses or verify laboratory values
- Incorrect storage of study drug
- Failure to follow up on subjects who drop out

Subjects with at least 1 deviation classified as "Important" and suspected to have an impact on the statistical analysis of study endpoints will be excluded from the PP Population. The final decision regarding classification of deviations and inclusion and exclusion of participants from the analysis populations will be based on a final listing of protocol deviations. Subject inclusion/exclusion in analysis populations will be determined during a blinded review meeting before study data are unblinded. Clinical and Biostatistics team members will provide input to the decision and the final composition of the analysis populations will be approved by the Sponsor.

Protocol deviations will be summarized by treatment group, subjects not randomized and overall subjects for the All Subjects population. Data will also be presented in a by-subject listing.

Additionally, inclusion and exclusion criteria not met and reasons for screen failures will be listed.

7.3. Demographics and Other Baseline Characteristics

Demographic variables will include race, ethnicity, age (based on date of informed consent), age categories (18-35 years, 36-55 years, 56-65 years), age at onset (from SAD Diagnostic Checklist), sex, height, weight, and body mass index (BMI).. Baseline variables will include average SUDS score at Visit 2 (Baseline), pre-IP SUDS score at Visit 2 (Baseline), average anticipatory SUDS score at Visit 2 (Baseline), and LSAS total score at Visit 1 (Screening).

Demographic and baseline characteristic data will be summarized for the Safety, ITT and PP Populations by treatment group (including subjects not randomized for the Safety population only) and overall subjects. Data will also be presented in a by-subject listing.

Medical and psychiatric history will be summarized for the Safety Population by treatment group and overall subjects, classified by system organ class (SOC) and preferred term. Data will also be presented in a by-subject listing, which will include SOC, preferred term, and the verbatim term.

Prior medications will be summarized by treatment group, subjects not randomized and overall subjects, by the number and percentage of subjects taking each medication and classified by ATC class and preferred term. This analysis will be conducted for the Safety population. Data will also be presented in a by-subject listing, which will include ATC Level 2 classification, preferred name, and verbatim name.

Results from the Mini-International Neuropsychiatric Interview (MINI) and SAD Diagnostic Checklist will be tabulated by treatment group, subjects not randomized and overall subjects for the Safety population and presented in a by-subject listing.

